## **Planned Analyses**

Manipulation check (Teen Emotion Mindset Measure): A Group (GEM, CONT) X Time (pre-manipulation, post-manipulation) ANCOVA will be conducted to test whether the mindset manipulation changes girls' mindsets about the malleability of emotion. It is expected that the GEM but not CONT group will show increases in their growth mindsets following the manipulation (Group X Time interaction). Similar analyses will be conducted for the 2- and 4-month follow-up mindset measures. The interaction here and in the following analyses will be decomposed by conducting paired comparisons within group. All analyses will adjust for relevant covariates.

**Hypothesis Set 1a (Brain activation):** Whole-brain and ROI analyses (MANCOVAs) will examine whether the GEM group relative to the CONT group shows (a) lower activation in the AMY contrasting the criticism vs. neutral videos in the immerse trials of the ECT, and the negative vs. neutral distractors in the go-nogo task (i.e., less **emotion reactivity**); and (b) stronger intrinsic and task-related connectivity between the AMY and the CC networks of interest (FPN and CON) contrasting the criticism videos in the reframe vs. immerse trials of the ECT, negative vs. neutral distractors in the go-nogo task, and during resting state (i.e., stronger **ER**).

**Hypothesis Set 1b (Behavioral modulation of emotion):** Analyses will examine whether a GEM predicts better behavioral modulation (attentional control) of emotion. A MANCOVA will be conducted to test whether the GEM relative to the CONT group is better able to ignore negative emotion (vs. neutral) distractors, resulting in faster RTs and better accuracy.

Hypothesis Set 1c (state negative affect, Emotion Regulation Strategies, Emotional Self-Efficacy Scale): To examine emotion reactivity, Group (GEM, CONT) X Time or Group X Trial ANCOVAs will be conducted to test whether the GEM relative to the CONT group reports less of an increase in negative affect (across the Trier) and less negative affect after the criticism vs. neutral videos in the immerse trials (ECT). To examine ER success, Group X Trial ANCOVAs will be conducted to test whether the GEM relative to the CONT group reports less negative affect after the criticism reframe vs. immerse trials (ECT). To examine ER strategies, a MANCOVA will be conducted to test whether the GEM relative to the CONT group reports using more proactive *in vivo* strategies during the Trier. To examine long-term effects on ER strategies, a similar MANCOVA will be conducted using the 2- and 4-month follow-up data on self-reported ER. To examine self-efficacy, a Group (GEM, CONT) X Time (pre-manipulation, post-manipulation) ANCOVA will be conducted to test whether the GEM relative to the CONT group shows bigger increases in self-efficacy.

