Study Protocol Official Title: Effect of Emotion Mindsets on Emotion Processing: A Multilevel Experimental Investigation NCT Number: 03978871 September 27, 2023

Research Design and Method

163 adolescent girls with a high FEM (≥.75 SD above the mean on a screening¹⁶) completed these procedures in a single session: (1) baseline measures (demographics, puberty, mindsets, self-efficacy); (2) computer lesson (random assignment to group); (3) post-lesson mindsets, self-efficacy; (4) pre-Trier affect; (5) Trier; (6) post-Trier measures; (7) emotional challenge task (ECT), go-nogo, and resting state in the scanner. The selected tasks provide a multi-level, multi-method assessment of emotion processing, including self-reported negative affect (Trier, ECT; Hyp. Set 1c), naturally occurring *in vivo* ER in response to an ecologically valid stressor (Trier; Hyp. Set 1c), use of an explicit ER prompt (ECT; Hyp. Set 1c), neural correlates of reactivity and regulation (ECT, gonogo; Hyp. Set 1a), neural recovery from emotional challenge (resting state; Hyp. Set 1a), and behavioral indexes of cognitive control (go-nogo; Hyp. Set 1b). At 2- and 4-month follow ups, girls completed via the Internet the mindset and self-efficacy measures and a self-report measure of ER in daily life.

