Girls completed a 25-minute computer lesson with audio-recordings. The **GEM** manipulation, adapted by our research team from a well-validated mindset manipulation⁶⁵⁻⁶⁸, involves 6 components: (1) Introduction: discussion of emotional experiences in teenagers; (2) Explanation of neuroplasticity, emphasizing the potential for changes in the brain and modification of emotions during adolescence; (3) Scientific evidence for the effect of ER training on mood improvement; (4) Comprehension assessments: brief factual quizzes and written summary of key points; (5) Vignettes and written testimonials: scenarios in which older youth describe challenging situations when they felt negative emotions and used growth mindsets to help regulate their emotions; and (6) Self-persuasion exercise: a. Girls read a hypothetical scenario about an emotional challenge and describe their likely thoughts and feelings; b. Girls imagine the same event happening to another (younger) teen and help them understand how they can change, integrating what they learned about malleability of the brain and emotion. The **CONT** condition involves a structurally similar session, with the same number and type of reading and writing activities, that focuses on general education about the brain⁷⁴.

Manipulation check. Before and after the lesson and at the follow-ups, girls completed a measure of mindsets about emotion, adapted from Tamir¹⁶ to focus on teens (e.g., "The truth is, teens have very little control over their emotions."). The original measure has well-established psychometrics and is distinct from mindsets about other personal attributes¹⁶. Pilot data support the validity of the revised measure and support a single emotion mindset factor, $\chi^2(47) = 125.82$, CFI = .97, SRMR = .032.

Self-efficacy. Before and after the lesson and at the follow-ups, girls completed measures of ER self-efficacy¹⁶.

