## **Statistical Design and Power**

Originally planned sample size: 150

Final sample size: 163 (due to scan problems in 13 participants)

**Power**. Power for ANCOVAs and MANCOVAs was calculated with  $G^*$ Power. Based on prior research, we expect a large effect size for the mindset manipulation and medium or medium-to-large effects on emotion processing (e.g., medium to large effects, including for Group x Time interactions, were found for biological stress responses). With N = 150, power to detect a medium or large manipulation effect (Group x Time interaction) is >.99. Power to detect a medium univariate or multivariate group effect is >.86. Power to detect a medium univariate or multivariate Group x Time interaction is >.99. Power to detect a medium indirect effect using Monte Carlo simulations in Mplus is >.99.

**MRI** data. MRI data were preprocessed with fMRIPrep v21.0.0 (Esteban et al., 2018; Esteban et al., 2020; RRID:SCR\_016216), a Nipype v1.6.1-based tool (Gorgolewski et al., 2011; Gorgolewski et al., 2018; RRID:SCR\_002502). All preprocessing was implemented via an internal HPC image processing pipeline hosted by the Beckman Institute for Advanced Technology (v0.5.0 https://pipeline-hpc.readthedocs.io/).

A fieldmap of B0-non-uniformity was estimated from two EPI reference images using the TOPUP method (Andersson, Skare, and Ashburner (2003); FSL 6.0.5.1:57b01774). T1-weighted (T1w) volumes were corrected for intensity non-uniformity using this fieldmap via N4BiasFieldCorrection v2.1.0 (Tustison et al., 2010) from ANTs v2.3.3 (Avants et al. 2008, RRID:SCR\_004757). These were used as T1w references throughout the workflow—and skull-stripped using antsBrainExtraction.sh v2.3.3 (using the OASIS30ANTs template). Brain tissue segmentation of cerebrospinal fluid (CSF) and white-matter (WM) were performed on the brain-extracted T1w using the FAST routine from FSL (FSL 6.0.5.1:57b01774, RRID:SCR\_002823, Zhang, Brady, and Smith 2001). Spatial normalization to the MNI152NLin6Asym template (Evans et al. (2012), RRID:SCR\_002823; TemplateFlow ID: MNI152NLin6Asym) was performed through nonlinear registration with the antsRegistration tool (ANTs v2.3.3) using brain-extracted versions of both T1w volume and template.

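### Mindset and self-efficacy are tested as change from the pre-lesson score; adjusting for that score answers the same question, usually more precisely (low priority)

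*SAP*

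**What the plan says.** Under Planned Analyses, the SAP's manipulation check reads: "A Group (GEM, CONT) X Time (pre-manipulation, post-manipulation) ANCOVA will be conducted to test whether the mindset manipulation changes" girls' mindsets. The interaction is named as the expected effect and is followed up by paired comparisons within each group. For later time points: "Similar analyses will be conducted for the 2- and 4-month follow-up mindset measures". Hypothesis Set 1c repeats the form: "To examine self-efficacy, a Group (GEM, CONT) X Time (pre-manipulation, post-manipulation) ANCOVA will be conducted". On adjustment, the SAP says only: "All analyses will adjust for relevant covariates". It lists none in these sections.

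The protocol's Research Design and Method gives the order of the session: "1) baseline measures (demographics, puberty, mindsets, self-efficacy); (2) computer lesson (random assignment to group); (3) post-lesson mindsets, self-efficacy; (4) pre-Trier affect". Both pre-lesson scores therefore precede assignment.

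Under Statistical Design and Power, the SAP says "we expect a large effect size for the mindset manipulation" and gives power above .99 for a medium or large Group x Time effect at N = 150. The final number of girls is 163.

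**The concern.** In a Group x Time model the pre-lesson score is one level of the outcome. With two levels of Time, the interaction F is the square of the t statistic comparing mean change between arms. This fixes the weight on the pre-lesson score at 1. Baseline adjustment estimates the weight from the data and so removes more noise unless 1 happens to be the best weight.

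Both analyses estimate the same GEM-minus-CONT effect, because randomisation makes the expected baseline difference zero. What is at stake is precision: wider intervals than the collected data allow, chiefly for self-efficacy and for any 2- or 4-month mindset effect smaller than the immediate one.

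**Working it through.** **Inputs.** From the SAP: N = 150 for power, and medium and large effects without numbers. Not in the documents and therefore assumed: 1:1 allocation (75 per arm), two-sided alpha .05, pre/post correlation rho, and k = pre-lesson SD / post-lesson SD. Effects are in post-lesson SDs.

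**The plan's own figures.** For a two-group, two-time interaction with f = .25 (the usual value for a medium effect, assumed here), lambda = f² x N x 2/(1 - rho) on F(1, 148).
- rho = 0: lambda = .0625 x 150 x 2 = 18.75, power .9904.
- rho = .3: lambda = 18.75/.7 = 26.79, power .9993.

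The stated >.99 therefore reproduces. So does the stated >.86 for a medium univariate group effect: lambda = .0625 x 150 = 9.375, power .8604.

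**What f = .25 means here.** With equal SDs, the noncentrality of a change-score comparison with difference d is d²/[2(1 - rho) x 2/75]. At d = 1.0 and rho = .3 this is 1/(1.4 x 2/75) = 26.79, the same lambda. So f = .25 in this routine is a 1.0 SD difference in change.

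**Relative precision.** Per-girl variance is 1 + k² - 2 rho k for change and 1 - rho² for the adjusted analysis. The ratio is (1 - rho²)/(1 + k² - 2 rho k), which becomes (1 + rho)/2 at k = 1. CI narrowing is 1 minus the square root of the ratio.

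| k | rho | Variance ratio | CI narrowing |
|---|---|---|---|
| 1.0 | .3 | .65 | 19% |
| 1.0 | .5 | .75 | 13% |
| 1.0 | .7 | .85 | 8% |
| 1.0 | .8 | .90 | 5% |
| 1.0 | .9 | .95 | 2.5% |
| 0.8 | .3 | .784 | 11% |
| 0.8 | .5 | .893 | 5.5% |
| 0.8 | .7 | .981 | 1% |
| 0.8 | .8 | 1.000 | 0 |

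The last row shows the general rule: there is no gain when k = rho. At k = 1.2 narrowing would be 27%/22%/18% at rho .3/.5/.7, but nothing in the documents points to a larger pre-lesson SD. At k = 1, a change-score test would need 150/.65 = 231, 150/.75 = 200 or 150/.85 = 177 girls to match the adjusted analysis at 150.

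**Power** (noncentral t, 75 per arm, k = 1, rho .3/.5/.7):
- 0.5 SD: change .73/.86/.975; adjusted .89/.94/.99.
- 0.8 SD: change .984 or more; adjusted .999 or more.
- 1.0 SD: change .999 or more, so adjustment adds almost nothing.

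If all 163 girls gave questionnaire data (81/82 assumed), 0.5 SD power is .77/.89/.98 (change) against .91/.96/.99 (adjusted). The variance ratios do not change.

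**Simulation** (75 per arm, slope estimated, 6,000 trials per cell). Under no effect at rho .5, rejection was .045 to .053 for change and .046 to .054 for adjusted. When k = rho, estimating the slope cost under 1% in variance.

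**Where the advantage can fail.** With a common slope, adjustment can lose if allocation is unequal and slopes differ. Take 2:1 allocation, pre-lesson variance 1, pre/post covariances .4 and 1.1, and post-lesson variances 1 and 1.5. The scaled variance is the sum over arms of (v - 2bc + b²)/p.
- Change (b = 1): 1.2 x 1.5 + 0.3 x 3 = 2.70.
- Adjusted (b = 2/3 x .4 + 1/3 x 1.1 = .633): .894 x 1.5 + .508 x 3 = 2.87.

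**The case against.** **The planned test is sound and matches the hypothesis.** The plan states its expectation as change, and the interaction tests that directly. This stands. A reader might infer that the test is biased or invalid, but randomisation and the simulated error rates show otherwise.

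**The plan already reports power above .99.** This also stands at the plan's apparent scale. A reader might infer that the figure is wrong, or that .73 to .975 is the power at the plan's own medium effect. Neither follows: the figure reproduces, and 0.5 SD is a separate assumption, half the difference in change implied by f = .25.

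**The gain may be small.** The pre- and post-lesson scores come from one session around a 25-minute lesson, so rho could exceed .7. Entry requires a high FEM at screening, which may shrink the pre-lesson mindset SD and bring k below 1. Both would reduce the gain for mindset over much of the range shown. Against this, the same selection may also lower rho, self-efficacy was not the stated selection variable, and rho may be lower at 2 and 4 months.

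**The analysis is already called an ANCOVA with relevant covariates.** That label does not supply the adjustment, because the pre-lesson score is already a level of Time. If the score were also entered as a covariate with its own Time interaction, the Group x Time test would equal the adjusted test, but the text does not say this. Part of the SAP was not available for this review, so a covariate list there cannot be excluded.

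**Conclusion.** The point holds as a low-priority improvement in precision. The planned Group x Time comparison is valid, and no stated figure is wrong. Adjusting for a baseline already collected gives equal or better large-sample precision if allocation is about 1:1 or slopes are equal across arms; the allocation ratio is not stated. With equal SDs the CI gain runs from about 19% at rho .3 to 2.5% at rho .9. It can be zero, and its true size cannot be learned from the documents. It is not safe to infer that adjustment always wins or that the manipulation check is underpowered.

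The benefit lies mainly with self-efficacy and with smaller follow-up mindset effects. For the follow-ups, the figures apply to a comparison of pre-lesson with one later time point, because the SAP does not say how many levels Time has there.

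**What to change.** Analyse post-lesson mindset, post-lesson self-efficacy, and 2- and 4-month mindset with group as factor and the pre-lesson score of the same measure as covariate. Alternatively, use a mixed model with a common baseline mean and unstructured covariance, which does not need equal SDs and keeps girls who miss one follow-up. Report the adjusted GEM-minus-CONT difference with a 95% CI at each time point, and keep the within-group paired changes as description. State the levels of Time in the follow-up analyses.

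Do not treat pre-Trier affect as a pre-randomisation baseline, since the protocol places it after the lesson. Self-efficacy was also collected at follow-up ("Before and after the lesson and at the follow-ups, girls completed measures of ER self-efficacy"), but the SAP's self-efficacy test names only pre and post, so modelling the later scores would be an addition.

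The cost is a few sentences in the SAP and a few lines of code on data already held. If the Group x Time results have been seen, keep the interaction as the planned test and report the adjusted estimate beside it, labelled as added later.

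### Within-arm paired tests are the only stated follow-up to the Group interactions, so a significant ECT interaction would not show on which trial type GEM and CONT differ

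*SAP*

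**What the plan says.** Under the manipulation check, the SAP specifies the inferential test: "A Group (GEM, CONT) X Time (pre-manipulation, post-manipulation) ANCOVA will be conducted to test whether the mindset manipulation changes girls' mindsets". The prediction is tied to that test: "It is expected that the GEM but not CONT group will show increases in their growth mindsets following the manipulation (Group X Time interaction". Then comes the follow-up rule: "The interaction here and in the following analyses will be decomposed by conducting paired comparisons within group". No GEM-CONT comparison at a time point or trial type is named as follow-up. The SAP also does not state that the decomposition depends on a significant interaction.

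Hypothesis Set 1c has the other analyses with an interaction. They are Trier negative affect (Group x Time), ECT reactivity, where GEM is expected to report "less negative affect after the criticism vs. neutral videos in the immerse trials (ECT"), ECT regulation success, which sets reframe against immerse trials ("Group X Trial ANCOVAs will be conducted to test whether the GEM relative to the CONT group reports less negative affect after the criticism reframe"), and self-efficacy (Group x Time).

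Other analyses are specified as direct group comparisons with no interaction named. These are Set 1a ("Whole-brain and ROI analyses (MANCOVAs) will examine whether the GEM group relative to the CONT group shows (a) lower activation in the AMY"), Set 1b ("A MANCOVA will be conducted to test whether the GEM relative to the CONT group is better able to ignore negative emotion") and the strategy analysis in Set 1c ("a MANCOVA will be conducted to test whether the GEM relative to the CONT group reports using more proactive" strategies). The follow-up rule has nothing to act on there.

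**The concern.** The hypotheses concern GEM relative to a randomised control, but the follow-up looks inside each arm separately.

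- **ECT ratings.** Both arms should feel worse after criticism than after neutral videos, so two significant paired tests are the likely result and say little about the lesson. A smaller criticism-neutral gap in GEM can come from lower ratings after criticism, which is the effect of interest, or from higher ratings after neutral videos, which is no benefit. Regulation success has the same ambiguity: a larger reframe-immerse gap can come from lower reframe ratings or from higher immerse ratings. By the Protocol's ECT definitions the two indices share the criticism-immerse trials, so a shift there moves both.
- **Pre/post measures.** The prediction of an increase in one arm and none in the other invites a reader to take one significant and one non-significant paired test as the evidence. That pattern is not a test of the group difference.

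At stake is the interpretation of a significant interaction. The validity of the interaction test is not in question.

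**Working it through.** **Inputs.** From the documents: random assignment (Protocol, Research Design and Method); planned N = 150, and power of >.86 for a medium group effect and >.99 for a medium Group x Time interaction (SAP, Statistical Design and Power). Assumed, because the documents do not give them: 1:1 allocation (75 per arm), two-sided alpha .05, medium effect f = 0.25 (d = 0.5), and correlation ρ between a girl's two measurements (.5 unless varied).

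**1. The plan's own power figures.**
- Group effect: λ = f²N = 0.0625 × 150 = 9.375 on 1 and 148 df gives power 0.860. This matches.
- Group x Time: λ = f²N × 2/(1 − ρ) gives 0.990 at ρ = 0, 0.9993 at .3 and 0.99998 at .5. This matches.
- Scale of that interaction: at ρ = .5, λ = 18.75/0.5 = 37.5. A difference δ in mean change, with change SD √(2(1 − ρ)) = 1, has λ = δ² × 75/2 = 37.5δ². The SAP's >.99 is therefore for δ = 1 SD. For δ = 0.5 SD, λ = 9.375 and power is 0.86.

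**2. ECT reactivity.** Assumed rating SD 1, ρ = .5, and a criticism-neutral gap of 1.5 in CONT and 1.0 in GEM; 20,000 simulated trials per scenario.

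| Test | A: GEM lowers criticism ratings by .5 | B: GEM raises neutral ratings by .5 |
|---|---|---|
| Group x Trial interaction significant | 86% | 86% |
| Paired test significant, GEM | 100% | 100% |
| Paired test significant, CONT | 100% | 100% |
| GEM-CONT on criticism trials significant | 86% | 5% |

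The planned tests give the same significance pattern in A and B; the GEM-CONT comparison by trial type does not. The same calculation applies to regulation success, with a .5 SD shift in either the reframe or the immerse cell: interaction 86%, both paired tests 100%.

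**3. Pre/post measures with no group effect.** Let both arms truly change by 0.25 SD, with ρ = .5.
- Each paired test has noncentrality 0.25 × √75 / 1 = 2.165 and power 0.570.
- P(GEM significant, CONT not) = 0.570 × (1 − 0.570) = 0.245.
- Over equal changes of 0.1 to 0.5 SD this probability runs from 1.0% to 24.5% at ρ = .5, from 4.7% to 24.6% at ρ = .3, and from 0.0% to 24.0% at ρ = .7.
- If a significant interaction is required first, it falls to 2.3% in the 0.25 SD, ρ = .5 case (200,000 simulated trials).

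**4. Both arms change, by different amounts.** With true changes of 1.0 SD in GEM and 0.5 SD in CONT, the interaction is significant in 86% of trials. In 98.8% of those, both paired tests are significant as well.

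**5. Power of a between-arm follow-up.** At d = 0.5 and 75 per arm it is 0.860 unadjusted. Adjusted for a baseline correlated .5, λ = 9.375/(1 − 0.25) = 12.5 on 1 and 147 df, and power is 0.940.

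**The case against.** A reader might infer from the rule that the trial cannot show whether GEM caused the predicted effects. The documents do not support that. The interaction being decomposed is the GEM-minus-CONT difference in change, or in the trial gap, and so it carries the randomised comparison. The SAP also ties the manipulation-check prediction to it. Nor does the rule reach every outcome, since the Set 1a, Set 1b and strategy MANCOVAs name no interaction.

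Further points stand in part:

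- **Order of steps.** Decomposing an interaction is naturally read as following a significant one. On that reading 2.3% is the relevant figure, and 24.5% applies only if the paired tests are read alone. The SAP does not state the condition.
- **Where the ambiguity can arise.** Mindset and self-efficacy are first measured before the lesson, so the lesson cannot have moved that value. For the Trier, the Protocol already describes reactivity as a residualised score. The problem is mainly one for the ECT.
- **The index is the study's own.** The Protocol defines reactivity as criticism versus neutral in immerse trials, and the interaction tests exactly that. Making a criticism-only difference a condition of success would redefine the index. It would also cost power: in scenario A, requiring both tests gives about 77% against 86% for the interaction alone.
- **Scenario B is hypothetical.** Nothing in the documents suggests that GEM would worsen responses to neutral videos, and the large assumed gaps make the 100% figures nearly automatic. The four cell means would also differ between A and B. Even so, the ambiguity is a property of any 2 x 2 interaction and does not depend on those values, and the plan does not call for a test or interval on the differences between arms.

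**Conclusion.** The concern holds as a gap in interpretation. For mindset, self-efficacy, Trier affect and ECT ratings, the only stated follow-up is within arm and does not show where GEM and CONT differ. The interaction tests and their stated power are unaffected. The consequence is greatest for the two ECT analyses, where both paired tests are likely to be significant and either cell could produce the interaction. For pre/post measures, a significant GEM test beside a non-significant CONT test must not be read as a group effect. Under equal true changes of 0.25 SD (ρ = .5) that pattern occurs in about 24.5% of trials if read alone and about 2.3% after a significant interaction. All these rates rest on assumed effect sizes, correlations, alpha and allocation. The structural point about the ECT does not.

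**What to change.** Keep the interaction as the inferential test and replace the follow-up sentence with:

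> Only significant Group interactions will be decomposed, by estimating the GEM-CONT difference with its 95% CI at each trial type (ECT), and at post-lesson, post-Trier or follow-up adjusted for the baseline value (Time analyses). Within-group changes are descriptive.

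Use the trial-type contrasts to interpret the interaction, not as a second criterion for success. For the Trier, the pre-task rating is taken after the lesson, so show the GEM-CONT difference at that point too.

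**Cost.** One sentence, with the same data and no change in N. It adds a few secondary contrasts, to be labelled as follow-up. For the ECT there are three distinct ones (criticism-immerse, neutral-immerse, criticism-reframe), because the two indices share a cell.

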- Emotional go-nogo. Girls completed a CC task with emotion distractors¹⁰⁹ depicting negative (social rejection), positive (social acceptance), or neutral (scrambled) images¹¹⁰. Letters were presented sequentially at the center of the screen, with distractors in the background. The distractors were presented alone (350ms), prior to the letter (750ms), to make them difficult to ignore. Girls were instructed to ignore the images and respond as quickly as possible without sacrificing accuracy with a button press to every letter (go trials), except for Xs (no-go; 25% of trials). Girls acquire a prepotent tendency to press and must inhibit their responses during X trials. Research supports the validity of emotional go-nogo tasks¹⁰⁹⁻¹¹¹. Reaction time (RT) and accuracy scores provide an index of ER.

2- and 4-month follow-ups. Youth completed the mindset measure, self-efficacy measures, and a measure to assess ER (e.g., cognitive reappraisal, rumination) in daily life. Items were drawn from existing measures¹¹²⁻¹¹⁷ or written for this measure. Pilot data in 158 adolescents support links between emotion mindsets and these self-reports of ER.

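### The follow-up emotion-regulation MANCOVA makes no stated use of partial responders' data; a likelihood model on all available waves would, at little cost

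*SAP*

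**What the plan says.** The only planned analysis of long-term ER is in the SAP, Planned Analyses, Hypothesis Set 1c: "a similar MANCOVA will be conducted using the 2- and 4-month follow-up data on self-reported ER". The analysis it resembles is the MANCOVA on ER strategies used during the Trier. The SAP does not say whether the two waves enter jointly, as a Time factor, or one at a time. The manipulation-check paragraph of the same section plans follow-up mindset analyses along the lines of its Group by Time ANCOVA.

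The Protocol (Research Design and Method) says that at follow-up "girls completed via the Internet the mindset and self-efficacy measures and a self-report measure of ER in daily life". The ER instrument is described as "a measure to assess ER (e.g., cognitive reappraisal, rumination) in daily life". Daily-life ER is not among the listed baseline measures.

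The SAP (Statistical Design and Power) gives "Originally planned sample size: 150", and a final 163 explained by scan problems in 13 participants. It states "Power to detect a medium univariate or multivariate group effect is >.86", computed at N = 150. The text available gives no follow-up completion rate, no attrition allowance and no rule for missing follow-up data. Part of the SAP was not available to this review, so a rule stated there cannot be excluded.

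**The concern.** The laboratory measures come from one session. The follow-ups are remote, and some girls may answer one wave and not the other. A standard MANCOVA needs a complete outcome vector for each girl.

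- **Both waves in one model:** a girl missing one wave also loses the wave she did answer.
- **One model per wave:** a girl missing month 4 is absent from the month-4 comparison, although her month-2 score carries information about it.

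On either reading, information already collected goes unused. Power on the only long-term ER outcomes may be lower than it need be, and the group contrast may be biased if dropout follows earlier ER differently in the two arms.

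**Working it through.** **Inputs from the documents:** N = 150 for power, final N = 163, a medium effect, stated power above .86.

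**Assumed, because the documents do not give them:** two-sided alpha .05, equal arms, d = .5 as medium (d = .4 as a smaller case), wave correlation r = .6, 10% to 25% missing per wave.

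**1. The plan's own figure.** A medium univariate effect is f = .25. With λ = N f² and a noncentral F on 1 and N − 2 df:
- N = 150: λ = 150 × .0625 = 9.375, power .860. The stated figure reproduces.
- N = 163: power .887.
- Power first falls below .80 at 127 girls, that is, once 36 of 163 (22%) are lost.

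**2. Power for the group difference in the two-wave mean.**

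Complete cases: the mean of two waves has variance (1 + r)/2 = .8, so the group difference has variance 4 × .8/n and λ = n d²/3.2. Power ≈ Φ(√λ − 1.96).

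All available data: information per girl is I = p_both S⁻¹ + diag(p_only2, p_only4), where S is the 2 × 2 correlation matrix. The variance is (4/163) a′I⁻¹a with a = (.5, .5), and λ = d²/variance.

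For 15% missing at month 2 and 25% at month 4:
- *Independent.* n = 163 × .85 × .75 = 103.9. Complete cases: λ = 103.9 × .16/3.2 = 5.20 at d = .4, and 8.12 at d = .5. All data (p_both .6375, p_only2 .2125, p_only4 .1125): variance .02193, λ = 7.30 and 11.40.
- *Monotone* (all who miss month 2 also miss month 4). n = 163 × .75 = 122.25. Complete cases: λ = 6.11 and 9.55. All data (p_both .75, p_only2 .10): variance .02371, λ = 6.75 and 10.54.

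| Missing (month 2/month 4) | Pattern | Complete cases | Girls with any wave | d = .4: complete vs all | d = .5: complete vs all |
|---|---|---|---|---|---|
| none | – | 163 | 163 | .81 vs .81 | .95 vs .95 |
| 10%/20% | monotone | 130 | 147 | .72 vs .76 | .89 vs .92 |
| 10%/20% | independent | 117 | 160 | .68 vs .78 | .86 vs .93 |
| 15%/25% | monotone | 122 | 139 | .70 vs .74 | .87 vs .90 |
| 15%/25% | independent | 104 | 157 | .63 vs .77 | .81 vs .92 |

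**3. If the MANCOVA is run per wave.** For the month-4 contrast at d = .4:
- 15%/25% monotone: n = 122.25, λ = 122.25 × .16/4 = 4.89, power .60. Using month-2 data, λ = 5.11, power .62.
- Month 2 complete, 20% missing at month 4: n = 130.4, λ = 5.22, power .63. Using month-2 data, the variance is (4/163)(.36 + .64/.8) = .02847, λ = 5.62, power .66.

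**4. A multivariate version of the loss.** Assume ten outcomes (five strategies at two waves) and f² = .15. Power of the complete-case test is .936 with all 163 girls. At 20% missing per wave it is .850 if the same girls miss both waves (n = 130), .730 if independent (n = 104), and .695 if different girls miss each wave (n = 98).

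**5. Bias.** Simulation with 4,000 replicates: N = 163, true effect .50 at both waves, r = .6, about 18% to 20% missing at month 4, month 2 complete.

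| Dropout depends on month-2 ER | Complete-case month-4 effect | Likelihood-type month-4 estimate |
|---|---|---|
| not at all | .50 | .50 |
| equally in both arms | .50 (.505) | .50 |
| in GEM only, moderate | .56 | .50 |
| in GEM only, stronger | .62 | .50 |

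Because month 2 is complete here, the complete cases are exactly the month-4 responders. The month-4 bias is therefore the same under a per-wave MANCOVA. Joint entry would also distort the month-2 effect, to .60 and .69 in the last two rows.

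**The case against.** The strongest reply is that the SAP never says partial responders are dropped and never says the two waves form one outcome vector. The model it refers back to has strategies at a single time point as outcomes, so one MANCOVA per wave is a natural reading. This stands: listwise deletion across waves is an inference from the method, not a stated rule. It does not remove the point, because the per-wave reading still leaves month-2 information unused for month 4 (step 3), though the gain there is only 2 to 3 points of power.

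Second, no attrition is documented. This also stands. The rates above are assumptions, and with complete follow-up the two approaches agree.

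Third, the power figures in step 2 are for a single two-wave mean, not for a MANCOVA across strategies. Correct; they show the relative loss on one score. Step 4 gives a multivariate counterpart, but it rests on an assumed number of outcomes and effect-size convention.

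Fourth, the gap depends on the missingness pattern. Under monotone dropout it is 3 to 4 points; the gaps of 7 to 14 points need independent missingness. The documents cannot say which applies.

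Fifth, fitting each strategy in its own mixed model gives up the omnibus test. Five independent tests at .05 would have familywise error 1 − .95⁵ = .23. This is a fair criticism of a simple replacement, and the fix below answers it.

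A reader might also infer that the planned analysis is biased as it stands. The documents do not support that. Complete-case analysis was unbiased in the simulation when dropout was unrelated to ER, or related to it equally in both arms. Nothing in the text shows arm-specific dropout, and the two lessons are described as structurally similar.

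**Conclusion.** The point holds as an inexpensive improvement in method, with a gap in specification. The SAP does not say how the waves enter the follow-up MANCOVA or how partial responders are treated, and on either reading of the text a standard MANCOVA leaves collected data unused.

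The size is conditional. With 15%/25% missing, N = 163 and r = .6, complete-case against all-data power for a two-wave mean runs from .70 vs .74 to .63 vs .77 at d = .4, and from .87 vs .90 to .81 vs .92 at d = .5. There is no difference if follow-up is complete. Bias in the group effect requires dropout that depends on earlier ER differently by arm. The likelihood analysis removes it only when missingness depends on observed data.

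It would go too far to conclude that girls were in fact dropped, that the long-term test is underpowered, or that its effect is inflated. The available text gives no completion figures from which to judge any of these.

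**What to change.** In the SAP (Planned Analyses, Hypothesis Set 1c, long-term effects, and the follow-up part of the manipulation check):

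- Analyse follow-up ER and the follow-up mindset measure with a likelihood-based model on all available observations, with Group, Time (2 and 4 months), Group by Time, the planned covariates and an unstructured covariance across waves.
- Keep the joint test across ER strategies with a multivariate mixed model or full-information maximum likelihood (FIML). Otherwise, model each strategy separately with a stated multiplicity correction.
- Report the group contrast at each wave and averaged over waves.
- Report completion by arm and wave.

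**Cost:** SAP wording, standard software and somewhat more complex modelling; no new data. The original MANCOVA can be kept as a secondary analysis. **Limit:** girls who miss both waves still contribute no follow-up ER outcome, since daily-life ER is not a listed baseline measure.
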